### 9.2.1.5 Number of Hours with Ventilator Use

The hypotheses of interest relating to the number of hours free from ventilator use (within 30 days) are as follows:

$$H_0: \mu_t = \mu_c$$

$$H_1: \mu_t \neq \mu_c$$

where  $\mu_t$  and  $\mu_c$  represent the mean number of hours in the treatment and control groups, respectively. The treatment groups will be compared with respect to the mean hours using a two-

sided two-sample t-test. Subjects that enter the study on ventilation are excluded from this endpoint analysis. Summary of this endpoint will include the mean, quartiles, median, minimum, maximum and standard deviation of hours for each treatment arm, a 95% confidence interval for the difference in the two treatment arm mean hours, and the p-value from the test described above.

#### 9.2.1.6 Number of Hours with Vasopressor Use

The hypotheses of interest relating to the number of hours with vasopressor use are as follows:

$$H_0: \mu_t = \mu_c$$

$$H_1: \mu_t \neq \mu_c$$

where  $\mu_t$  and  $\mu_c$  represent the mean number of hours in the ICU in the treatment and control groups, respectively. The treatment groups will be compared with respect to the mean hours using a two-sided two-sample t-test. Summary of this endpoint will include the mean, median, quartiles, minimum, maximum and standard deviation of hours for each treatment arm, a 95% confidence interval for the difference in the two treatment arm mean hours, and the p-value from the test described above.

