7.3.2 Secondary Endpoints

Secondary endpoints to be evaluated:

1. Length of ICU stay (days) until subject is medically ready for discharge
2. Number of hours free from ventilator use
3. Requirement for mechanical ventilation
- 4.
5. Number of hours free from vasopressor use
6. Changes in serum creatinine levels from baseline
7. Requirement for renal replacement therapy (RRT)
8. Mean volume of fluid between the two treatment groups
9. Incidence of Major Adverse Cardiac Event (MACE)
10. Incidence of Adverse Events (AE)
11. Number of ICU readmissions
12. 30 day in-hospital Mortality rate
13. Discharge location
14. Mean difference in fluid balance at ICU discharge

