12.4 Secondary and Exploratory Endpoints

Secondary objectives that have been pre-specified to be included in the formal statistical analysis will be tested in sequential fashion using the Holms step-down procedure for type-I error rate correction if and only if the primary objective passes according to the criteria outlined above. At the conclusion of the trial, the key secondary endpoints will be ordered sequentially from most significant to least significant. The endpoints will then be tested in order at adjusted levels of significance (i.e. E1: 0.05/k, E2: 0.05/k-1; E3: 0.05/k-2, where k=number of specified endpoints). Once an endpoint fails, all following endpoints will not be tested. Following is a list of key secondary endpoints:

Following is a list of key secondary endpoints for formal testing:

- Length of ICU stay (days) until subject is medically ready for discharge
- Number of days free from ventilator use (30 day period)
- Requirement for mechanical ventilation
- Number of days free from vasopressor use
- Changes in serum creatinine levels from baseline
- Requirement for renal replacement therapy (RRT)

Additional secondary endpoint have also been identified for testing, but will not be included in the formal statistical testing procedures for key secondary endpoints:

- Incidence of Adverse Events (AE)

- Number of ICU readmissions
- Mortality rate
- Mean volume of treatment fluid
- Incidence of Major Adverse Cardiac Event (MACE)
- Discharge location
- Mean difference in fluid balance at ICU discharge

Additional sub-analyses have been planned for the primary and key secondary endpoints. Primary and secondary endpoints will also be evaluated by the following subgroup analysis:

- Patient disease state
- Patients determined to be fluid responsive vs non-fluid responsive
- AKI measures in patients determined to increase serum creatinine levels from baseline vs decrease serum creatinine levels from baseline
- Enrollment time frame

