#### 4.2.2 SECONDARY ENDPOINTS

##### 4.2.2.1 For formal testing

Key secondary endpoints for the purposes of formal statistical testing are:

- Changes in serum creatinine level from baseline to 72 hours (key secondary endpoint)
- Requirement for renal replacement therapy (RRT)
- Requirement for ventilator use
- Length of ICU stay (days) until subject is medically ready for discharge
- Number of hours with ventilator use (30-day period)
- Number of hours with vasopressor use

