### 7.5 MULTIPLE COMPARISONS AND MULTIPLICITY

It is recognized that with a multiplicity of tests comes inflation in the chance of a false finding. Therefore, formal statistical testing will only be done for the following secondary endpoints:

- Changes in serum creatinine level from baseline to 72 hours (key secondary endpoint)
- Requirement for renal replacement therapy (RRT)
- Requirement for ventilator use
- Length of ICU stay (days) until subject is medically ready for discharge
- Number of hours with ventilator use (30-day period)
- Number of hours with vasopressor use

These endpoints will be tested in a hierarchical (sequential) manner in the order given above (and testing will only proceed if a significant beneficial treatment effect is detected in the primary endpoint). Specifically, the first secondary endpoint (change in creatinine) will be compared between treatments at a two-sided 0.05 level of significance. If significant in the direction favoring Starling SV, then Starling SV will be considered beneficial on change in serum creatinine level, and the next endpoint (ICU stay) will be compared between treatments at a two-sided 0.05 level of significance; otherwise the statistical testing will stop and Starling SV will not be considered statistically significantly beneficial on any secondary endpoint. If the treatment comparison is able to proceed to this next secondary endpoint of ICU stay, it will be carried out at the two-sided 0.05 level of significance. If the treatment comparison is significant in the direction favoring Starling SV, then Starling SV will be considered beneficial on this endpoint and testing will proceed in a similar manner for the remaining endpoints; otherwise, treatment comparisons will stop and Starling SV will not be considered beneficial on this second secondary endpoint of ICU stay nor on all endpoints after it in the above sequence.

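### The SAP tests hours on vasopressors instead of the protocol's vasopressor-free time, with no window or death rule, so early death shortens the score and the comparison can be biased either way

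*SAP*

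**What the plan says.** **Protocol.** The synopsis and section 7.3.2 list "Number of hours free from vasopressor use". Section 12.4, which names the endpoints for formal testing, has "Number of days free from vasopressor use". Neither gives a period or says how a death is scored.

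**SAP.** Sections 2, 4.2.2.1 and 7.5 list "Number of hours with vasopressor use", and 9.2.1.6 sets it up for testing: "The hypotheses of interest relating to the number of hours with vasopressor use are as follows". No period is given, although the ventilator-hours endpoint in the same lists has 30 days. Section 9.2.1.6 says the symbols in the hypotheses "represent the mean number of hours in the ICU in the treatment and control groups, respectively", which is not the quantity in its own title. It then says: "The treatment groups will be compared with respect to the mean hours using a two-sided two-sample t-test".

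**Deaths.** Section 9.2.1.6 is silent. ICU stay (9.2.1.4) has its own rule: deaths in the ICU are censored. SAP 7.3 names death as one cause of missing observations and says missing data are not imputed, but does not say whether a death makes vasopressor hours missing.

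**Population and order.** Efficacy is analysed on the per-protocol (PP) set, with mITT supportive (SAP 6.3, 6.4, 9). PP requires 72 hours of monitoring in the Starling arm only. In SAP 7.5 vasopressor hours is last of six secondaries, each tested at two-sided 0.05 only if the primary and every earlier secondary favour Starling.

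**The concern.** Turning free time into time on treatment matters in a population where deaths are expected. Patients have sepsis with refractory hypotension, and 30-day in-hospital mortality is itself an endpoint. Hours on vasopressors end at death, so a short value can mean early recovery or early death, and a t-test on the raw hours treats the two alike. Fewer hours is the direction that counts as benefit.

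The missing window and death rule also leave the result open to choice. One analyst could count hours to death, another could treat deaths as missing, and a third could borrow the censoring rule from ICU stay. The estimates would differ, and the SAP would not settle which was planned. SAP 6.5 openly marks a change from the protocol on the safety population. Nothing comparable is said here, so a reader cannot tell whether this change was intended.

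**Working it through.** The plan gives no assumed value, effect or power for vasopressor hours, so there is no stated figure to reproduce for this endpoint. All vasopressor and mortality inputs below are assumptions. From the SAP come the arm sizes (80 Starling, 40 control) and the two-sided 0.05 t-test.

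**Scoring one patient**

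| Patient | SAP: hours on | Free hours over 30 days (720 h), death = 0 |
|---|---|---|
| Dies at 10 h, still on vasopressors | 10 | 0 |
| Survivor weaned at 40 h | 40 | 720 − 40 = 680 |

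The SAP score ranks the death as better. The second column ranks it as worse, but only because a window and a death score have been added.

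**Group means, all randomised patients kept**

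Assume need is exponential with mean m in both arms (no true difference), deaths fall uniformly between 6 and 72 h, and hours on = min(need, time of death). The expected shortening per death is

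L = m² × (e^(−6/m) − e^(−72/m)) / 66

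- m = 40: 1600 × (0.8607 − 0.1653) / 66 = 16.9 h
- m = 60: 3600 × (0.9048 − 0.3012) / 66 = 32.9 h

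The bias towards the arm with more deaths is (mortality difference) × L. False-claim rates come from 20,000 simulated trials per row.

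| m | Mortality, Starling v control | Bias | Significant for Starling, this test alone |
|---|---|---|---|
| 40 h | 30% v 20% | 0.10 × 16.9 = 1.7 h for Starling | 4.9% |
| 40 h | 30% v 15% | 0.15 × 16.9 = 2.5 h for Starling | 5.9% |
| 60 h | 30% v 20% | 0.10 × 32.9 = 3.3 h for Starling | 5.6% |
| 60 h | 30% v 15% | 0.15 × 32.9 = 4.9 h for Starling | 7.4% |

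Repeat runs of the last row reached 7.8%. The nominal rate is 2.5%. With equal 20% mortality the simulated rate is 2.8-2.9%, the small excess arising with skewed hours and unequal arms.

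**Same inputs, early Starling deaths removed by the PP monitoring rule**

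Every simulated death falls at or before 72 h, so on a literal reading all Starling deaths leave and control deaths stay. The Starling mean is then m and the control mean is m − (control mortality) × L.

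| m | Control mortality | Bias | Significant for Starling (Starling mortality 30%) |
|---|---|---|---|
| 40 h | 20% | 0.20 × 16.9 = 3.4 h for control | 0.9% |
| 40 h | 15% | 0.15 × 16.9 = 2.5 h for control | 1.1% |
| 60 h | 20% | 0.20 × 32.9 = 6.6 h for control | 0.6% |
| 60 h | 15% | 0.15 × 32.9 = 4.9 h for control | 0.9% |

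The sign reverses. Starling mortality does not enter the expected bias, because those patients are gone.

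**Sensitivity to timing of death**

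A second model uses lognormal need (mean 60 h, log-SD 0.8), exponential death times, mortality 30% v 20%, all patients kept, and 5,000 trials. Negative values favour Starling.

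| Mean time to death | Hours on = min(need, death) | On vasopressors until death |
|---|---|---|
| 24 h | −4.1 h | −3.6 h |
| 48 h | −3.2 h | −1.3 h |
| 120 h | −2.0 h | +5.9 h |

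Dropping Starling deaths before 72 h from this model (mean time to death 24 h) gives 59.9 h Starling v 51.8 h control, or 8.1 h in favour of control.

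**The case against.** A reader might infer that more early deaths on Starling would earn a formal claim of benefit. The documents do not support that. The primary set is PP, and on a literal reading its monitoring rule removes early Starling deaths, which turns the bias towards control and puts false Starling claims below nominal. The claim also needs the primary, creatinine, RRT, ventilator requirement, ICU stay and ventilator hours all to succeed first. The 5-8% rates are for this test alone and are an upper limit on the chance of a false formal claim under those inputs.

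A reader might also infer that the protocol's measure handled death correctly and the SAP undid it. The protocol has no window and no death rule either. If free time were simply a fixed window minus hours on vasopressors, an early death would look just as good. Restoring the protocol's name is therefore not enough.

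Counting hours to death is one reading of a silent section, since SAP 7.3 could be taken to make deaths missing. That would compare survivors only, which is not a randomised comparison. The large gap on free hours is mostly the assumed mortality gap restated: 0.10 × (720 − 40) = 68 h. It shows that the score points the right way but says nothing about vasopressors. Mortality is also reported separately with Kaplan-Meier curves (SAP 9.2.2.3), which limits the chance that a difference in deaths goes unseen.

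All of this stands. It limits the size and direction of the claim. It does not supply the missing window, death rule or correct parameter.

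**Conclusion.** The concern holds as a defect of definition. The SAP swaps the protocol's endpoint for its opposite without saying so, leaves the period and the scoring of death open, and misstates the tested means. Taken literally, the t-test compares values cut short by death.

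The bias has no fixed direction. Under the assumed inputs it is about 2 to 5 h towards the arm with more early deaths if all randomised patients are kept, and about 2.5 to 6.6 h towards control if early Starling deaths leave PP (8.1 h in the second model). With all patients kept, late deaths on vasopressors can also reverse the sign. None of the mortality, vasopressor or timing inputs comes from the documents.

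Because the endpoint is last in a gatekept sequence, a false formal claim is a minor risk. The main harm is that the arm means, the 95% interval and the p-value in the report could mislead in either direction. The change should be made, but the primary conclusion does not depend on it.

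**What to change.** In SAP 2, 4.2.2.1, 7.5 and 9.2.1.6:

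- Define the endpoint as vasopressor-free hours over a fixed period, for example 30 days, in line with the ventilator endpoint and 30-day in-hospital mortality.
- Score in-hospital deaths within that period as zero free hours.
- State how patients discharged before the end of the period are counted. The protocol synopsis collects outcomes only to hospital discharge, so keeping the death rule to in-hospital deaths avoids new follow-up.
- Include all randomised patients for this endpoint, whatever their duration of monitoring.
- Correct the definition of the tested means, and record the change from the protocol with its reason.
- Report hours on vasopressors descriptively, split by survivors and deaths, next to mortality.

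The cost is mainly SAP wording, settled before unblinding, because vasopressor start and stop times are needed for either measure. Keeping all randomised patients departs from the SAP's PP-first rule for this one endpoint and should be stated as such. The downside is that free hours combine mortality with vasopressor duration and can be driven by mortality, so the two components should also be shown separately.

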### 9.2.2 NOT FOR FORMAL TESTING

#### 9.2.2.1 Incidence of Treatment Emergent Adverse Events (AE)

A Treatment Emergent Adverse Event (TEAE) is one that started or worsened in severity during or after randomized treatment was attempted. The number and percentage of patients with incidence of at least one TEAE will be summarized by treatment arm in a table. The summary will include the number and percent of subjects experiencing one or more AEs cumulatively up to 72 hours, one week, and 30 days. Though no formal hypothesis tests are planned, 95% confidence intervals for the difference in rates between the two arms at each time point will be completed and included using the normal approximation to the binomial distribution.

The analysis will be repeated for serious TEAS. In addition, the number and percentage of patients with at least one TEAEs will be presented by severity and relationship to study procedure; patients with more than one TEAE will be categorized according to the maximum severity and maximum relationship experienced.

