10. SAFETY/DEVICE ASSESSMENT

10.1 Adverse Events

Subjects will be carefully monitored during the study for possible device related adverse events (AEs). The investigator or designee will determine AE occurrences and collect the required data. It is anticipated that the occurrence of device related adverse events will be a low number. All device related adverse events will be reviewed not only by the site investigator, but also by the sponsor's medical officer.

Serious Adverse events will be collected during the 72 hour (+ 48 hours) treatment period in the following areas: Cardiac, CNS, pulmonary, renal, and skin disorders.

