10.2 Reporting Procedures

10.2.1 General Reporting Requirements

All device related adverse events must be recorded on the Adverse Event eCRF by the investigator (or designee). The report should include: start date of the adverse event, treatment,

resolution, and assessment of both the seriousness and the relationship to the investigational device.

The following criteria must also be adhered to by the Investigator:

- Completion of separate device related Adverse Event forms to document each event
- The forms must be signed by the Investigator, and
- Supplying to the Sponsor (or designee), upon Sponsor's request, with any additional information related to the safety reporting of a particular event

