#### 9.2.2.5 Incidence of Major Adverse Cardiac Event (MACE)

The incidence of MACE through to 72 hours, one week, and 30 days will be summarized by treatment arm in a table. The summary will include the number and percent of subjects by arm by category. Though no formal hypothesis tests are planned, 95% confidence intervals for the difference in rates between the two arms will be completed and included using the normal approximation to the binomial distribution or Wilson method (if an observed rate is less than 10% in any treatment group). Kaplan-Meier curves of time to first component of MACE will be presented by treatment group.

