### 10.1 ALL TREATMENT EMERGENT ADVERSE EVENTS

The number of TEAEs and the number and percentage of patients with at least one TEAE, with at least one device-related TEAE, with at least one serious TEAE and with at least one device-related TEAE will be presented by treatment group. These summaries will be presented for TEAEs occurring from start of treatment through 72 hours, from 72 hours through Discharge, from Discharge through 30 days, and from the start of treatment through 30 days.

The number of TEAEs and the number and percentage of patients with at least one TEAE will be presented for each treatment group by MedDRA system organ class and preferred term. This analysis will be repeated for serious TEAEs (collected through 72 hours only), device-related TEAEs, and AEs leading to withdrawal from the study.

In addition, the by-treatment number and percentage of patients with at least one TEAEs will be presented by severity and relationship to study procedure within each system organ class and preferred term; patients with more than one TEAE within a given system organ class and preferred term will be categorized according to the maximum severity and maximum relationship experienced.

A listing of all adverse events will include the subject number, AE number, days since index procedure, the AE SOC and PT, the severity of AE, whether the AE is classified as serious (SAE), the relationship of the AE to the investigational device or procedure, the action taken, the outcome, and the adjudication status.

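### SAP safety summaries at one week, at 30 days and after discharge run past the AE and SAE collection that the protocol schedules, and the collection passages conflict with each other

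*SAP*

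**What the plan says.** **What will be reported.** SAP 9.2.2.1 summarises, by arm and with 95% confidence intervals for the difference, the subjects with "one or more AEs cumulatively up to 72 hours, one week, and 30 days". It then adds: "The analysis will be repeated for serious TEAS". SAP 10.1 tabulates TEAEs from start of treatment to 72 hours and also "from 72 hours through Discharge, from Discharge through 30 days, and from the start of treatment through 30 days". For MACE, SAP 9.2.2.5 states: "The incidence of MACE through to 72 hours, one week, and 30 days will be summarized by treatment arm in a table", and it adds Kaplan-Meier curves.

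**What will be collected.** In the protocol's Table 1 (section 9.4), the adverse events row is marked only under the enrollment-to-72-hours column, with 48 hours added. The cell for 72 hours to discharge is blank, and there is no column after discharge. Protocol 10.1 states: "Serious Adverse events will be collected during the 72 hour (+ 48 hours) treatment period in the following areas", and names five: cardiac, CNS, pulmonary, renal and skin. Protocol 10.2.1 sets the form requirement: "All device related adverse events must be recorded on the Adverse Event eCRF".

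**A third window for serious events.** SAP 10.1 refers to "serious TEAEs (collected through 72 hours only", and closes the bracket there.

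**Wider protocol text.** Section 10.1 also says that subjects are monitored for device-related AEs throughout the study. Section 10.2.2 requires every SAE to be reported, with no limit of time or organ system. Section 12.2.1 has AEs reported for all enrolled subjects up to study exit.

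**The concern.** The SAP plans safety tables for periods in which the protocol's schedule has no adverse event collection. The AE summaries are counts and percentages by arm, with no rule for follow-up time or censoring, and SAP 7.3 does not impute missing data. In a table of that kind, a subject with no form is ordinarily counted as event-free, although the SAP does not say so. A 30-day percentage built on five days of collection would look like a low 30-day rate with a confidence interval around it.

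Scope is a second problem. SAP 9.2.2.1 speaks of all TEAEs, whereas the protocol requires the AE form for device-related AEs and collects SAEs in five areas. A rate built on that scope cannot be read as an all-cause comparison with standard of care.

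The third is the serious-event window. The SAP says that these events are collected for 72 hours, yet reports them at one week and 30 days.

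**Working it through.** The documents give no AE or MACE rate to reproduce. The check therefore compares the windows and then illustrates the size.

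**1. Collection and reporting side by side**

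| Source | Events | Period |
|---|---|---|
| Protocol Table 1 | Adverse events | 72 h + 48 h; blank from 72 h to discharge; no later column |
| Protocol 10.1 | SAEs, five areas | 72 h + 48 h |
| Protocol 10.1 | Device-related AEs | Throughout the study, no hour limit |
| Protocol 10.2.2 | All SAEs | No limit stated |
| Protocol 12.2.1 | AEs, all enrolled | To study exit |
| SAP 10.1 (collection) | Serious TEAEs | 72 h |
| SAP 9.2.2.1 (reporting) | TEAEs and serious TEAEs | 72 h, one week, 30 days |
| SAP 10.1 (reporting) | TEAEs | To 72 h; 72 h to discharge; discharge to 30 days; to 30 days |

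Two results need no choice between the protocol passages. First, the 72-hour statement in SAP 10.1 conflicts with the extra 48 hours in Protocol 10.1 and with the serious-event summaries in SAP 9.2.2.1. Second, no passage schedules AE collection after hospital discharge. The synopsis collects outcome data up to that point, yet SAP 10.1 gives discharge to 30 days its own summary.

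**2. Elapsed time covered**

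Table 1 window: 72 + 48 = 120 h. One week is 168 h and 30 days is 720 h.

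- 120/168 = 71% and 120/720 = 17%
- With a 72 h window: 72/168 = 43% and 72/720 = 10%

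**3. Share of true incidence captured**

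Let R be the true 30-day risk and H = -ln(1 - R). Cumulative incidence at t hours is F(t) = 1 - exp[-H(t/720)^k], with k = 1 for a constant hazard and k = 0.5 for a front-loaded one. R and k are assumptions. Nothing is taken as recorded after the window closes.

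For R = 20%, H = 0.223:

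- k = 1: F(120) = 1 - exp(-0.223 × 0.167) = 3.7%; F(168) = 1 - exp(-0.223 × 0.233) = 5.1%
- k = 0.5: F(120) = 1 - exp(-0.223 × 0.408) = 8.7%; F(168) = 1 - exp(-0.223 × 0.483) = 10.2%

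| k | R | True one-week | Recorded by 120 h | Share of one-week | Share of 30-day |
|---|---|---|---|---|---|
| 1 | 10% | 2.4% | 1.7% | 72% | 17% |
| 1 | 20% | 5.1% | 3.7% | 72% | 18% |
| 1 | 40% | 11.2% | 8.2% | 73% | 20% |
| 0.5 | 10% | 5.0% | 4.2% | 85% | 42% |
| 0.5 | 20% | 10.2% | 8.7% | 85% | 44% |
| 0.5 | 40% | 21.9% | 18.8% | 86% | 47% |

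With collection to 72 h only, the same models capture about 43-68% of one-week and 10-37% of 30-day incidence.

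**The case against.** A reader might infer that the protocol collects events only to 120 hours and that the later rates must therefore be falsely low. The documents do not support that. Protocol 10.1 has no hour limit for device-related AEs, 10.2.2 asks for all SAEs, and 12.2.1 runs to study exit. Table 2 (section 13.5) asks for subject deaths within 24 hours of knowledge, and section 9.3.3 records events such as cardiac arrest and CPR. The SAP was also written from case report forms that are not among the documents, and it places the final analysis after 30-day follow-up. Its 72-hour remark concerns serious events alone, which may mean that its authors expected other AEs to be collected for longer. All of this stands: the protocol contradicts itself, and understatement depends on which text the sites followed.

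It is equally tempting to apply the AE row of Table 1 to MACE. MACE is a separate secondary endpoint, is not defined, and has no stated collection window. Some of its events may be captured as outcome data up to hospital discharge.

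These summaries are outside formal testing, and the SAP says that the study is not meant to support a regulatory filing. That limits the consequence.

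The objection does not remove the mismatch. Table 1 and the SAE sentence in Protocol 10.1 are the passages that set a specific window, and SAP 6.5 flags a change of AE population but no change of AE window or scope. If sites followed different passages, the later rates would mix follow-up lengths, which is also a defect.

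**Conclusion.** The SAP's AE and SAE summaries at one week, at 30 days, from 72 hours to discharge and from discharge to 30 days go beyond the protocol's scheduled collection. The SAP's own serious-event window contradicts both the protocol and the SAP's later summaries. These points rest on the text alone and should be corrected.

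Understatement is conditional. If the 120-hour window was applied and simple percentages were used, about 72-86% of one-week and 17-47% of 30-day incidence would be recorded. That range rests on assumed 30-day risks of 10-40%, on two assumed hazard shapes, and on no reporting after 120 hours. The one-week column would be affected moderately and the 30-day column severely.

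For MACE, the documents support only that its definition and window are missing. If collection does stop at day 5, its Kaplan-Meier curves would run flat from there unless subjects are censored at that point. Type I error, power and sample size are unaffected.

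**What to change.** - **Protocol and SAP:** reconcile Protocol Table 1, 10.1, 10.2.1, 10.2.2 and 12.2.1 with SAP 9.2.2.1 and 10.1, so that one collection window and one scope are stated for AEs and one for SAEs.
- **SAP 9.2.2.1 and 10.1:** limit the summaries to the window actually collected, or censor at its end, and drop columns for periods without collection. Change the 72-hour statement for serious TEAEs to match the reconciled window.
- **Table labels:** name the scope collected, for example device-related AEs, or SAEs in the collected areas.
- **SAP 9.2.2.5:** define MACE and state its collection window. Keep the one-week and 30-day rates and the Kaplan-Meier curves only if events are collected that long, and censor at the end of collection.

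The cost is wording in the SAP, the table shells and the safety sections of the protocol. Some later safety columns may be lost. If the reconciled text and the case report forms show that collection ran to discharge or to day 30, the columns for those periods can stay.
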